3.3 Study Duration and Dates

This is a phase 1, two-period, two-treatment, crossover study. Subjects will be screened within 28 days of the initiation of study drug dosing. Eligible subjects who consent to the study will be randomly assigned to 1 of 2 groups, each group will receive both treatments alternately, in a crossover fashion (two-period, two-treatment crossover design), with the two treatment periods separated by a 7-day washout period.

In treatment period 1, subjects will be admitted to the clinic on day 0, the day before dosing, and will stay in the clinic until 48 h post-dose. In treatment period 2, subjects will be admitted to the clinic on day 7, the day before dosing, and will stay in the clinic until 48 h post-dose. The scheduled visits and procedures for each visit are provided in [Appendix 1](#).

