4.2 Inclusion Criteria

Each subject must meet the following criteria to be enrolled in this study.

1. Subjects who are between 18-65 years of age inclusive with body-mass index (BMI) between 18.0 kg/m² and 32.0 kg/m², inclusive.
2. Male subjects who are surgically sterile or male subjects who are not surgically sterile must agree to refrain from donating sperm and use appropriate birth control such as the use of condoms when engaging in sexual intercourse for a period of 30 days after discharge from the clinic.
3. Female subjects of childbearing potential who are willing to use an adequate method of contraception and to not become pregnant for the duration of the study.
4. Female subjects who are surgically sterile (hysterectomy, oophorectomy) or postmenopausal (absence of menses greater than 12 months and age > 45 years) are eligible if they test negative on the urine pregnancy test.
5. Subjects who are non-smokers for at least 3 months prior to screening.
6. Subjects with adequate venous access at multiple sites in both arms.
7. Subjects who are willing and able to be confined to the clinical research facility as required by the protocol.
8. Subjects who have the ability to comprehend and willingness to provide written informed consent in accordance with institutional and regulatory guidelines.

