4.3 Exclusion Criteria

Subjects who meet any of the following criteria will be excluded from the study.

1. Subjects who are determined by the investigator or sub-investigator to be unsuitable for participating in the study based on medical conditions, including impairment of the central nervous system, circulatory system, respiratory system, blood/hematopoietic function system, gastrointestinal system, liver/kidney function, thyroid function, pituitary function and/or adrenal function.
2. Female subjects who are nursing or pregnant.
3. Subjects with a clinically significant history of allergy to drugs or latex.
4. Subjects with a history of alcohol or drug dependence in the last 12 months.
5. Subjects who had 400 mL of whole blood collected within four months or 200 mL of whole blood collected within one month of the screening test.
6. Subjects who had blood component collection within 14 days prior to the screening test.
7. Subjects who have used prescription or over-the-counter (OTC) drugs within 14 days prior to the first dose.

8. Subjects who have used vitamin preparations or supplements (including St. John's Wort and ginseng) within 14 days prior to the first dose.
9. Subjects who have undergone strenuous activity within 72 hours prior to Day 1 in each period.
10. Subjects who are unable (e.g., food intolerance) or unwilling to consume a high-fat breakfast within 25 minutes.
11. Subjects who have been treated with an investigational drug within 30 days or 7 half-lives of the investigational drug, whichever is longer, prior to the first dose of study drug in this trial.
12. Subjects who had previously received EGT0001474 or bexagliflozin, or any other SGLT2 inhibitors within 3 months from the screening.
13. Subjects whose screening electrocardiogram (ECG) demonstrates any one of the following: heart rate > 100 bpm, QRS > 120 msec, QTc > 470 msec (corrected by Bazett's formula), PR > 220 msec (a subject with PR > 220 msec will generally be excluded but exceptions may be allowed at the discretion of the investigator), or any rhythm that is not sinus rhythm, sinus bradycardia, or sinus arrhythmia.
14. Subjects whose sitting blood pressure is above 140/90 mmHg at screening.
15. Subjects who have a positive result of HBsAg antigen, HCV antibody, urinary drug or urinary cotinine test.
16. Subjects with known human immunodeficiency virus (HIV) disease.

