6.9.3 Pregnancy

Women of childbearing potential (WOCBP) who are sexually active must use an effective method of birth control during the course of the study, in a manner such that risk of failure is minimized.

Before enrolling WOCBP in this clinical trial, investigators must review guidelines about study participation for WOCBP. The topics should generally include:

1. General information.
2. Informed consent form.
3. Pregnancy prevention information.
4. Drug interactions with hormonal contraceptives.
5. Contraceptives in current use.
6. Guidelines for the follow-up of a reported pregnancy.

Prior to study enrollment, WOCBP must be advised of the importance of avoiding pregnancy during trial participation and the potential risk factors for an unintentional pregnancy. The subject must sign an informed consent form stating the above-mentioned risk factors and that the consequences were discussed with her.

During the study, all WOCBP should be instructed to contact the investigator immediately if they suspect they might be pregnant (e.g., missed or late menstrual cycle).

If a subject or investigator suspects that the subject may be pregnant prior to investigational product administration, the investigational product administration must be withheld until the results of serum pregnancy tests are available. If the pregnancy is confirmed, the subject must not receive the investigational product and must not remain in or be enrolled in the study.

The investigator must notify the Medical Monitor within 3 working days of the receipt of information that any female subject who has become pregnant. This reporting requirement will continue until 4 weeks after the last investigational product exposure.

The investigator must record the event on the Pregnancy Surveillance form and forward it to the sponsor's clinical or designated personnel.

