7 STUDY ACTIVITIES

7.1 Screening (Days -28 to -1)

During the screening period, the following information will be gathered and the indicated procedures will be performed:

- Explain the content of informed consent to the subject and collect signed informed consent.
- Medical history and demographic information obtained.
- Perform a physical examination, including height and weight measurements as described in [Section 6.3](#).
- Vital signs collected including: pulse, temperature, respiratory rate, and blood pressure taken in the sitting position after at least 5 min of rest as described in [Section 6.4](#).
- 12-lead ECG taken in the supine position after at least 10 min of rest as described in [Section 6.5](#).
- Clean-catch, mid-stream urine will be collected for urinalysis as described in [Section 6.6.2.2](#). If urine is dipstick positive for leukocyte esterase or nitrites, sample is to be sent for microscopic evaluation and culture.
- Urine screen for drug abuse and cotinine. If the drug screen is conducted more than 5 days pre-dose, the drug screen must be repeated prior to dosing. Drug abuse testing includes amphetamines, barbiturates, cocaine metabolites, opiates, benzodiazepines, and cannabinoids.
- Women will receive urine pregnancy test.
- Blood will be drawn for hematology, serum chemistry, and serology as detailed in [Section 6.6.2.1](#).
- The inclusion/exclusion criteria will be evaluated based on the information collected at the screening examination.

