7.2 Clinic Admission (Day 0)

- On day 0 the following information will be gathered and the indicated procedures will be performed:
- If screening was conducted more than five days prior to dosing, the inclusion and exclusion criteria must be confirmed and a urine drug screen performed.
- A partial physical examination must be performed as described in [Section 6.3](#).
- If the subject is still eligible based on the study inclusion and exclusion criteria the subject will be admitted and randomized into the study.
- Concomitant medications and adverse event information will be collected as appropriate
- Pre-dose urine collection in 12 h batches at -12 h to 0 h (on day 0) for baseline analysis of electrolytes, uric acid and creatinine and for UGE (PD) analysis as described in [Section 6.6.2.3](#).

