7.5 Day 7 Activities

On day 7 the following information will be gathered and the indicated procedures will be performed:

- If the subject is still eligible based on the study inclusion and exclusion criteria, the subject will be admitted for the cross-over phase of the study.
- Concomitant medications and adverse event information will be collected as appropriate.

Pre-dose urine collection in 12 h batches at -12 h to 0 h (day 1) for baseline analysis of electrolytes, uric acid and creatinine and for UGE (PD) analysis as described in [Section 6.6.2.3](#). Subjects who are terminated from the study at this time must have the reason for termination entered onto the case report form.

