Appendix 1 Schedule of Events

[figure not shown]
Study activity	Screening		Period 1					Period 2			
	D -28 to -1	D0	D1 pre-dose	D1 post-dose	D2	D3	D7	D8 pre-dose	D8 post-dose	D9	D10
Medical history and ICF	X										
Screening for I/E criteria ¹	X	X					X				
Physical exam ²	X	X									X
Demographics	X										
Randomization		X									
Admission and discharge		X				X	X				X
Vital signs ³	X		X	X	X	X		X	X		X
ECG ⁴	X		X	X				X	X		X
Urinalysis ⁵	X		X			X		X			X
Blood draw for clinical lab tests ⁶	X		X			X		X			X
Blood sample for PK ⁷			X	X	X	X		X	X	X	X
Urine Collection ⁸		X	X	X	X	X	X	X	X	X	X
Urine Pregnancy Test	X										
Adverse event and concomitant medication		X	X	X	X	X	X	X	X	X	X
Study termination											X

[figure not shown]
1. Subject compliance with inclusion and exclusion criteria will be verified at check-in of each period (on day 0 and day 7).
2. Weight and height will be recorded as part of the physical examination. Height will be recorded once at screening only. A complete physical exam (PE) will be performed at screening and day 10 prior to discharge.
3. Vital signs include: pulse, body temperature, respiration rate, systolic and diastolic blood pressure. On days 1 and 8, vital signs will be determined at pre-dose and at 4 h and 48 h (day 3 or 10) post-dose.
4. 12-lead ECG will be conducted after 10 min of rest. ECG data will be recorded at screening, on days 1 and 8 at pre-dose and at 4 h post-dose and when clinically indicated.
5. Clean sample to be collected at each visit. If urine is dipstick positive for leukocyte esterase or nitrites, sample is to be sent for microscopic evaluation and culture. Urine drug screen will be performed on screening visit only. If screening is conducted more than 5 days prior to dosing, drug screening shall be repeated.
6. Blood samples at the designated visits for clinical chemistry and hematology parameters are listed in [Table 2](#).
7. Plasma samples for the PK profile of bexagliflozin will be collected at pre-dose and at 1, 2, 3, 4, 5, 6, 8, 10, 12, 16, 24, 36, and 48 h post-dose.
8. Urine collection for urinary glucose (PD), electrolytes, uric acid & creatinine are described in Section 6.6.2.3.

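### The only scheduled pregnancy test is at screening, so a woman could be dosed on a result up to 28–29 days old at dose 1 and 35–36 days old at dose 2

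*Protocol*

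**What the plan says.** **Who may enrol.** Protocol 4.2 admits "Female subjects of childbearing potential who are willing to use an adequate method of contraception" and who will not become pregnant during the study. Protocol 4.3 excludes "Female subjects who are nursing or pregnant".

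**When pregnancy is tested.** Protocol 7.1, at screening: "Women will receive urine pregnancy test". The schedules in Protocol Appendix 1 and SAP Table 1 each mark that test once, in the screening column. Protocol Table 3 allows for one 2 mL sample. The activity lists for Day 0 (7.2), Day 1 pre-dose (7.3), Day 7 (7.5) and Day 8 pre-dose (7.6) contain no pregnancy test.

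**How old screening may be.** Protocol 3.3: "Subjects will be screened within 28 days of the initiation of study drug dosing". Section 7.1 and Appendix 1 label the window Day -28 to Day -1, followed by a separate Day 0.

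**What happens at check-in.** Appendix 1, footnote 1: "Subject compliance with inclusion and exclusion criteria will be verified at check-in of each period (on day 0 and day 7". Under 7.2, if still eligible, "the subject will be admitted and randomized into the study". Under 7.5, on the same condition, "the subject will be admitted for the cross-over phase of the study". The only laboratory test tied to this re-check is the urine drug screen, repeated before the first dose when screening is more than five days old.

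**Other safeguards.** Protocol 6.9.3 requires effective contraception, counselling with signed consent, and prompt contact with the investigator if a woman thinks she may be pregnant. It also has a conditional rule: "If a subject or investigator suspects that the subject may be pregnant prior to investigational product administration", the dose is held until serum results are available. A woman with a confirmed pregnancy must not be dosed.

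**The concern.** Pregnancy is an exclusion that can begin between screening and dosing, and it can be present at screening but too early for the test to detect. Eligibility is checked again at both admissions, but no test is scheduled to support that check for this criterion. A site that follows the plan exactly could therefore give a woman one or both doses while she is unknowingly pregnant, against the intent of 4.3 and 6.9.3.

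The people exposed would be healthy volunteers who gain nothing medically from the drug. The issue is participant safety: the food-effect model, its confidence intervals and the urinary glucose comparison do not depend on it.

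**Working it through.** **1. The plan budgets exactly one test.** The urine rows of Protocol Table 3 (volume × number of samples) are urinalysis 10 × 6 = 60, PD 20 × 10 = 200, drug screen 10 × 1 = 10 and pregnancy test 2 × 1 = 2. The sum is 60 + 200 + 10 + 2 = 272 mL, which reproduces the stated total. The single screening test is therefore consistent across 7.1, Table 3, Appendix 1 and SAP Table 1, so a missing mark in one table does not explain it.

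**2. Age of the result at each dose.** Age = dose day − test day. Doses are on Day 1 and Day 8.

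| Timing of test | Age at dose 1 | Age at dose 2 |
|---|---|---|
| Day -28, Appendix 1 calendar with a Day 0 | 1 − (−28) = 29 days | 8 − (−28) = 36 days |
| 28 days before first dose, Protocol 3.3 reading | 28 days | 28 + 7 = 35 days |
| Day -1, latest screening | 1 − (−1) = 2 days | 8 − (−1) = 9 days |
| Added tests on Day 0 and Day 7 | 1 − 0 = 1 day | 8 − 7 = 1 day |

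The synopsis describes the washout as at least 7 days, so the ages at dose 2 in the first three rows would rise if period 2 started later than Day 8.

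**3. Whether another provision closes the gap.**

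- *Re-verification at check-in.* Footnote 1 does not say that every criterion is re-tested. The inclusion criterion that mentions a negative urine test (4.2, criterion 4) concerns sterile and postmenopausal women. The criterion for women of childbearing potential (criterion 3) names no test.
- *Section 6.9.3.* Contraception lowers the chance of a new pregnancy but does not detect one. It is required during the study, with no stated lead-in before screening, so it does not address a conception shortly before the screening test. The instruction to contact the investigator and the serum test both depend on suspicion.
- *Repeat drug screen.* It serves another purpose and does not cover dose 2. It shows only that repeating a urine test at check-in is practicable.

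No scheduled procedure would therefore detect an unsuspected pregnancy before either dose.

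**4. Urine volume with the added tests.** 60 + 200 + 10 + 3 × 2 = 276 mL, an increase of 4 mL.

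**The case against.** The strongest reply is that this is a suggestion, not an error. The plan nowhere promises a repeat test, and the investigator is free to do one when confirming eligibility. Contraception, counselling and the missed-cycle instruction all operate between screening and dosing, and an interval of about four weeks gives some women time to notice a late period. The worst-case ages measure how old the result is, not the risk: the ages can be as low as 2 and 9 days, the number of women of childbearing potential could be zero, and no pregnancy probability or reproductive-toxicity figure is available. Exposure is two single 20 mg doses of a drug with a mean half-life of about 8 to 10 hours. Finally, a urine test can miss a very early pregnancy on Day 0 or Day 7 just as at screening. Subjects are confined until 48 hours after the first dose, so a conception between the check-ins would fall in roughly Day 3 to Day 7, when a Day 7 test is least able to show it.

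Much of this stands. There is no contradiction, the remaining risk cannot be quantified, and the added tests reduce the gap without eliminating it. The Day 0 test matters more. The Day 7 test is useful mainly for a pregnancy that was too early to show on Day 0 and has had seven more days to become detectable.

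None of it supplies a scheduled test before dosing. A test that the investigator may choose to do is not a safeguard in the plan, and the suspicion-based rule cannot work where there is no suspicion.

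**Conclusion.** The concern holds as a participant-safety gap in the schedule. A pregnancy result may be up to 28 or 29 days old at dose 1 and up to 35 or 36 days old at dose 2, against 1 day at each dose with check-in testing. These are maxima: they assume screening at the start of its window and dosing on Days 1 and 8.

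The point applies only to women of childbearing potential, whose number the documents do not give and which lies between 0 and 18. No probability of exposure is claimed. The change should be made because the exposure is avoidable at very low cost. It has no bearing on the sample size or on the PK and urinary glucose analyses.

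**What to change.** - Add a urine pregnancy test for women of childbearing potential at Day 0 and Day 7 in Protocol Appendix 1, 7.2 and 7.5, and in SAP Table 1.
- Require a negative result before randomisation on Day 0 and before dosing on Day 8.
- State that a positive urine result counts as suspicion under 6.9.3, so dosing is held pending the serum test.
- Change Table 3 to three pregnancy tests, which raises the urine total from 272 to 276 mL.
- Reword SAP 8.4.6, which lists only results from before treatment, so that the Day 7 result is clearly included.

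**Cost.** Two extra 2 mL urine tests per woman of childbearing potential, at check-ins where urine is already collected. There is no added visit, and no added blood draw unless a positive urine result leads to the serum test. A positive result would delay or stop that woman's dosing, in line with 6.9.3.

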**CHANGE LOG FOR CHANGES MADE AFTER THE INITIAL APPROVAL**

Revision Date**	Section(s) Modified	Brief Description of Revision(s) or Reason(s) for Revision	Modifications Reviewed and Approved by*
			Sponsor, Everest

\* Provide person's initial and last name.

\*\* Update the Last Revision Dates on the cover page and the document header.

**GLOSSARY OF ABBREVIATIONS**

Abbreviation	Term
AE	Adverse Event
ALB	albumin
ALT	alanine aminotransferase
ANOVA	analyses of variance
AST	aspartate aminotransferase
ATC	anatomic therapeutic class
AUC	area under the plasma concentration-time curve
AUC extr	extrapolated area under the plasma concentration-time curve
AUC 0-∞	area under the plasma concentration-time curve from Time 0 to infinity
AUC 0-t	area under the plasma concentration-time curve from Time 0 to Time t
BLOQ	below the limit of quantitation
BMI	body mass index
BP	blood pressure
BUN	blood urea nitrogen
Ca	calcium
Cl	creatinine chloride
C last	concentration corresponding to T last
CL/F	apparent oral clearance
cm	centimeter
C max	maximum observed plasma concentration
CRF	case report form
CV	coefficient of variation
DBP	diastolic blood pressure
dL	deciliter
DM	data management
ECG	electrocardiogram

Abbreviation	Term
FDA	Food and Drug Administration
FPG	fasting plasma glucose
h	hour(s)
HBsAg	hepatitis B surface antigen
HCO 3	Bicarbonate
Hct	hematocrit
HCV	hepatitis C virus
HDL-C	high density lipoprotein cholesterol
Hgb	hemoglobin
ICF	informed consent form
IRAE	immediately reportable adverse event
K	potassium
kg	kilogram
KR	Kenward-Roger
L	liter
$\lambda_z$	terminal elimination phase rate constant
LDL-C	low density lipoprotein cholesterol
LLN	lower limit of normal
LS	Least square
MCH	mean corpuscular hemoglobin
MCHC	mean corpuscular hemoglobin concentration
MCV	mean corpuscular volume
MedDRA	Medical Dictionary for Regulatory Activities
mg	milligram
min	minute

Abbreviation	Term
mL	milliliter
msec	millisecond
Na	sodium
NCA	non compartmental analysis
OTC	over the counter
PCS	potentially clinically significant
PD	pharmacodynamic
PE	physical examination
PK	pharmacokinetic
PR	The period that extends from the beginning of the P wave (the onset of atrial depolarization) until the beginning of the QRS complex (the onset of ventricular depolarization).
PT	preferred term
QA	quality assurance
QC	quality control
QRS	The combination of three of the graphical deflections seen on a typical electrocardiogram.
RBC	red blood cell (count)
REML	restricted maximum likelihood
RR interval	intra-beat interval
SAE	serious adverse event
SAP	statistical analysis plan
SBP	systolic blood pressure
SD	standard deviation
SOC	system organ class
SOP	standard operating procedure
T ½	apparent terminal elimination half-life

---

Abbreviation	Term
TC	total cholesterol
TEAE	treatment emergent adverse event
TG	triglycerides
T last	time of last measurable (positive) concentration
TLF	table, listing, figure
T max	time of maximum observed plasma concentration
T-wave	Repolarization of the ventricles
UGE	urinary glucose excretion
ULN	upper limit of normal (value)
V z /F	apparent volume of distribution
WBC	white blood cell (count)
WHO-DD	World Health Organization Drug Dictionary

---

## **1. INTRODUCTION**

This Statistical Analysis Plan (SAP) outlines the statistical methods for the display, summary and analysis of data collected within the scope of Theracos Sub LLC protocol THR-1442-C-481 version 2 dated 20-May 2016. As with any SAP, the proposed methods and approaches to the data analysis should be deemed as flexible. The analysis of the data should allow changes in the plan to the extent that deviations from the original plan would provide a more reliable and valid analysis of the data. As such, the statistical analysis to a certain degree is iterative since much of the planning is based on assumptions that require verification. The purpose of this plan is to provide general guidelines from which the analysis will proceed. Nevertheless, deviations from these guidelines must be substantiated by a sound statistical rationale.

This SAP should be read in conjunction with the study protocol and the Case Report Forms (CRFs). This version of the SAP has been developed using the final version of the protocol mentioned above and the final version of the annotated CRFs dated 30-Jun-2016.

The SAP details the analysis of the data collected in the study and the presentation of the results of the analyses. The table, listing, and figure (TLF) shells are displayed in a companion document which provides information on the layout of the data displays.

All statistical analyses will be performed using SAS® version 9.3. Adverse events will be coded using the latest version of the Medical Dictionary for Regulatory Activities (MedDRA version 19.0 or newer).

This is a single center, phase 1, open-label,  $2 \times 2$  crossover study designed to assess the effects of a high-fat meal on the pharmacokinetics (PK) of orally administered bexagliflozin tablets. Approximately 18 eligible healthy subjects are planned to be randomized into two treatment groups such that an equal number ( $n = 9$ ) of subjects will receive a single oral dose of 20 mg of bexagliflozin with or without a meal on treatment day 1. Subjects randomized to receive bexagliflozin with a high-fat meal on day 1 will receive a second dose of bexagliflozin without a meal on treatment day 8 after an overnight fast. Subjects randomized to receive bexagliflozin without a meal on treatment day 1 after an overnight fast will receive a second dose of bexagliflozin with a high-fat meal on treatment day 8.

(See Protocol Sections 3.1 to 3.3 for details).

